3.1.4. Joint and Skin Related Adverse Events

Based on comprehensive review of the related rVSVΔG-ZEBOV-GP vaccine (17, 26, 38-43), a small percentage of subjects (approximately 5%) may experience post-vaccination arthritis with onset typically within one week of injection and resolving within days to weeks. The reported incidence by studies ranges from 0% to 23.5%, depending on the study methodology, definition of arthritis and method and timing of diagnosis. Arthritis may affect small or large joints, or the axial skeleton. Skin rash has been reported in 4% of subjects, commonly described as maculopapular or vesicular (33, 44). Subjects with suspected or confirmed diagnosis of post-vaccination arthritis (day 5 onwards) or petechial, purpuric, or vesicular rash or mucosal ulcers will be promptly evaluated according to standardized algorithms by Investigators trained on these case definitions. The algorithm for assessment of joint-related AEs is found in Figure 2 and the one for rash is found in Figure 3. A baseline serum sample will be stored at the immunology laboratory for use with the evaluation if needed.

Assessments may include some or all of the following:

- Targeted assessment of affected musculoskeletal areas.
- Detailed assessment of the involved joints to determine if joint aspiration is likely to yield joint fluid for further analysis.
- Full body evaluation for skin lesions and mucosal lesions (ulcers).
- At the discretion of the Investigator, and when feasible and acceptable to the subject, synovial fluid aspiration of at least one involved joint by a healthcare provider who is proficient in performing arthrocentesis in the affected joints. Arthrocentesis has only been required in rare cases in prior trials using this rVSV backbone (26).
- At the discretion of the physician, and when feasible and acceptable to the subject, 1 or 2 punch biopsies will be obtained of any petechial or purpuric rash. Biopsy has only been required in rare cases in prior trials using this rVSV backbone.
- Further laboratory evaluations from samples collected on days 1 and 29, and unscheduled samples to coincide with onset and resolution of symptoms:
 - Blood samples
 - o Chemistries (creatinine, blood urea nitrogen [BUN], uric acid)
 - o C-reactive protein (CRP)
 - Cytokines
 - o Rheumatoid factor (RF), anti-cyclic citrullinated peptide (CCP), anti-nuclear antibody (ANA)
 - o C3, C4
 - Urinalysis
- Skin biopsy of affected skin lesions (histopathology, RT-qPCR).
- Needle aspiration of vesicular skin lesions for RT-qPCR and virus isolation.
- Swab samples of mucosal lesions (e.g., mouth ulcers) for RT-qPCR.

- Synovial fluid assessment:
 - Cell count with differential
 - o Crystal examination
 - o Culture for bacteria, and virus isolation
 - o RT-qPCR for vaccine viral RNA
- Exploratory analyses may be performed on other bodily fluids. These data (as available) will be provided in listings.

3.1.5. Primary Immunogenicity Endpoints

The primary immunogenicity endpoints are as follows:

- Geometric mean titers (GMT) of Marburg GP protein-specific IgG antibody as measured by (ELISA on days 1 and 29.
- PsVNT₅₀ and PsVNT₈₀ MARV GP-specific neutralizing antibodies titers (with 50% and 80% neutralization, respectively) as measured by PsVNA on days 1 and 29.

3.1.6. Secondary Immunogenicity Endpoints

- GMT Marburg GP protein-specific IgG ELISA antibody on all other study days through Day 181
- Average PsVNT₅₀ and PsVNT₈₀ on all other study days to Day 181.
- Seroconversion rate (at least 4-fold increase in Marburg GP-specific IgG (ELISA)
- Seroconversion rate (at least 4-fold increase in Marburg GP-specific neutralizing antibody titer PsVNA)
- Geometric mean fold increase in Marburg GP-specific IgG (ELISA)
- Geometric mean fold increase in Marburg GP-specific neutralizing antibody titer (PsVNA)
- Reverse cumulative distribution of titers (IgG ELISA and PsVNA)

3.1.7. Exploratory endpoints

- Wild-type Marburg neutralization against one or more Marburg lineages
- Marburg ELISA against one or more Marburg lineages
- Determination of Fc-mediated cell-targeting vaccine-specific antibodies, e.g., ADCC, ADNP, ADMP, etc.
- Vaccine-specific T-cell responses to Marburg GP protein by intracellular cytokine staining (ICS) and/or enzyme-linked immune absorbent spot (ELISPOT)
- Determination of Marburg IgM ELISA antibody responses
- Determination of vaccine-specific pro-inflammatory markers, such as CRP, ICAM-1, VCAM-1 levels, and cytokine levels
- Determination of vaccine-specific gene activation by RNA transcript sequencing (transcriptomics)

• Determination of B or T cell responses to VSV proteins

3.1.8. Immunogenicity Endpoint Collection

Samples for immunogenicity testing will be collected per the Schedule of Events (Table 2). All subjects will have samples tested for serum Marburg GP-specific IgG ELISA and PsVNA.

3.2. OVERALL STUDY DESIGN

This Phase 1, FIH study of the Marburg vaccine candidate PHV01 is on the critical path for development of a VSV-vectored, single-dose vaccine for the prevention of Marburg virus disease. The purpose of the PHV01-C-101 study is to test the safety and immunogenicity of the plaque-purified, vaccine injected by the IM route undiluted (Group C: 1x10⁷ pfu in 1 mL) and at tenfold dilutions (Group B: 1x10⁶ in 1 mL and Group A: 1x10⁵ pfu in 1 mL) (Table 1). A blinded ascending dose design will be used in cohorts, such that lower doses are given first to 3 Pioneer vaccinees and a randomized placebo control (Group D: 1 mL Lactated Ringer's solution), with day 8 safety assessments reviewed before proceeding to higher doses in the next cohorts (Figure 1). Note: As this is a FIH study, a maximum of 2 randomized subjects will be dosed per day in Cohort #1. The ROG and a randomized placebo control will then be dosed at the lower dose, randomized with 3 Pioneer vaccinees and a placebo control at the next higher dose.

This trial of PHV01 will provide timely safety, immunogenicity, and dose-response data to guide further manufacturing, control, and clinical development of the vaccine. This trial will accelerate the development and availability of validated immunologic assays required to reliably define and qualify immunologic test methods and will guide dose selection for a subsequent Phase 2 trial in one or more endemic countries in Africa. An IA will be performed on the safety and serological data from all subjects collected up to day 29. The final Clinical Study Report (CSR) will be based on the safety and immunogenicity data collected on days 1-181. The schedule of assessments is provided in the Schedule of Events (SoE) (Table 2).

Table 2: Schedule of Events

	Visit 1	Visit 2	Visit 3	Visit 4	Visit 5	Visit 6	Visit 7	Visit 8	Visit 9
Visit # and Timing	-28to -1	Day 1	Day 2	Day 4 ± 1 day	Day 8 ± 1 days	Day 15 ± 2 days	Day 29 ± 2 days	Day 85 ± 7 days	Day 181 ± 7 days
Informed consent ¹	X								
Inclusion/exclusion	X	Review							
Demographics ²	X								
Medical history	X								
Vital signs ³	X	$X \times 2^3$	X	X	X	X	X	X	X
Physical exam	X	X^4	X ⁴	X ⁴	X ⁴	X ⁴	X	X^4	X ⁴
TEAEs, SAEs, MAAEs, AESIs ⁵	X	$X \times 2$	X	X	X	X	X		
Concomitant medications ⁵	X	$X \times 2$	X	X	X	X	X		
Pregnancy test ⁶	X	X					X		
Screening for HIV, HCV, HepB (5 mL) ⁷	X								
Rapid antigen test for SARS-CoV-2		X							
Hematology, chemistry, and coags (10.7 mL) ⁸	X	X		X	X		X		
HLA-B27 Testing		X							
Urinalysis ⁹	X			X	X		X		
MARV antibody tests (2 x 10 mL) ¹⁰		X			X	X	X	X	X
Blood for research (100 mL) ¹¹								X	
PBMC/T-cell Assay ¹²		X			X		X		
Transcriptomics (2.5mL PaxGene RNA tube) ¹³		$X \times 2$	X	X	X	X			
MARV viremia (7 mL) and shedding ¹⁴		$X \times 2$	X	X	X	X	X		
Cytokine levels (10mL) ¹⁵		X		X	X		X		
Vaccination		X							
Post-vaccination observation ¹⁶		X							
Provision of emergency contact card		X							
Training and review of Memory Aid		X	X	X	X	X	X	X	X

Abbreviations: AESI = Adverse Event of Special Interest; eCRF = electronic case report form; HBsAg = hepatitis B surface antigen; HCG = human chorionic gonadotropin; Hct = hematocrit; HCV = hepatitis C; HepB = hepatitis B; HgB = hemoglobin; HIV = human immunodeficiency virus; INR = international normalized ratio; MAAE = medically attended adverse event; RBC = red blood cell; PBMC = peripheral blood mononuclear cell; PCR = polymerase chain reaction; PT = prothrombin time; PTT = partial thromboplastin time; SAE = serious adverse event; TEAE = treatment emergent adverse event; WBC = white blood cell.

Footnotes:

- ¹ Obtain written informed consent for participation in the clinical study, clinical samples, and HIV testing.
- ² Demographic data include age, height and weight (for BMI), race, and ethnicity.
- ³ Vital signs will include blood pressure and pulse while seated and at rest, and body temperature measured orally. On Visit 2, vital signs will be assessed up to 60 minutes before vaccination, then at 60-90 minutes after vaccination and at $6h \pm 1h$. (Shown as $X \times 2$)
- ⁴ Directed physical examination at discretion of Investigator. See the Protocol for the Arthritis Pathway algorithm for subjects with joint complaints. If rash is present on any visit, the PI should reference the Dermatology Pathway.
- ⁵ SAEs, MAAEs, and AESIs will be recorded from day of consent until EOS. AEs will be recorded beginning with Screening. All TEAEs will be recorded from dosing on day 1 through day 29, and during the rest of the study. Concomitant medications will be recorded up to 6 months prior to study entry and throughout the duration of the study. This will include dietary supplements and other prophylactic substances.
- ⁶ Pregnancy tests (serum HCG) will be done in all female subjects at Screening. Repeat pregnancy tests (urine) will be done in all female subjects prior to vaccination and at day 29.
- ⁷ Screening serology will include HIV-1, HIV-2, HCV, and HBsAg.
- ⁸ Clinical laboratory assessments will include CBC (HgB, Hct, RBC, platelets), WBC with differential, metabolic chemistry panel, PT, PTT, and INR.
- ⁹ Urinalysis assessments by dipstick. Reflex testing by microscopy for abnormal blood or leukocyte esterase.
- ¹⁰ Two 10 mL tubes for serology: minimum of 6 (1.5 mL) aliquots of serum frozen. Four tubes will be used for viremia and neutralization studies and two tubes will be preserved at baseline and held for possible AE assessment. Collect one 10 mL tube for Rheumatologic or Dermatologic baseline
- ¹¹ Blood collection for serology and purification of IgG (100 mL). 10 × 10 mL SST tubes to be centrifuged, then the serum should be split as 10 mL aliquots in each of 5 x 15 mL conical sterile tubes and frozen at -60°C.
- ¹² Collect 6 × 10 mL EDTA tubes for PBMC separation and cryopreservation.
- ¹³ Collect in 2.5 mL PaxGene RNA tube for transcriptomics before dosing, then at 6h (± 1h) and on each subsequent visit as indicated.
- ¹⁴Blood (7 mL) for plasma, saliva (swab) and urine sample for virus detection before dosing, then at 6h (± 1h) and on each subsequent visit as indicated.
- ¹⁵ Blood (10 mL) for plasma cytokines, aliquoted into 4 × 1 mL cryotubes and frozen at -60°C.

Table 3: Blood Collection Volume Estimates

Blood Volumes	Volumes	D -28 to -1	Day 1	Day 2	Day 4	Day 8	Day 15	Day 29	Day 85	Day 181	Total
Blood for HepB, HepC, HIV (5 mL)	5.0	5.0									5.0
HLA-B27 testing	5.0		5.0								5.0
Safety Labs (10.7 mL)	10.7	10.7	10.7		10.7	10.7		10.7			53.5
Blood for MARV antibody tests (2 x 10 mL)	20.0		20.0			20.0	20.0	20.0	20.0	20.0	120.0
Blood for assay development (100 mL)	100.0								100.0		100.0
Blood for PBMC/T-cell Assay (6 x 10 mL)	60.0		60.0			60.0		60.0			180.0
Blood for RNA (2.5mL PaxGen tube)	2.5		2.5	2.5	2.5	2.5	2.5				12.5
Blood for viremia (7 mL)	7.0		14.0	7.0	7.0	7.0	7.0	7.0			49.0
Blood for Cytokine levels (10 mL)	10.0		10.0		10.0	10.0		10.0			40.0
	Totals	15.7	122.2	9.5	30.2	110.2	29.5	107.7	120.0	20.0	565.0

¹⁶ Includes TEAEs and examination of injection site 60-90 minutes after vaccination.

3.3. MEASURES TAKEN TO MINIMIZE/AVOID BIAS

3.3.1. Randomization

This is a single-blind study, with group assignment hidden from site staff (apart from the compounding pharmacist) and subjects, along with a blinded CRA who will monitor the site records. To further avoid the potential for bias, the Medical Monitors (Sponsor and CRO) will remain blinded as well, until the database is frozen for the interim analysis (IA). Randomization will be stratified to achieve balance of sex across PHV01 dose levels and placebo recipients. For each randomization number, 2 replacement subject randomization numbers will be generated. The treatment assignment for replacement subjects will be the same as the subject who is being replaced.

Study personnel will obtain treatment identification (ID) numbers from the Interactive Web Response System (IWRS) as eligible subjects, who have successfully completed the screening process and are deemed eligible to participate by the PI (or another designated Investigator), are enrolled and proceed to vaccination.

Care will be taken to ensure that recruiting and screening processes are unbiased with regard to race and gender. To maintain randomization, alternates will be used, if necessary, in the order in which they were deemed eligible. Alternates are allowed to join the next cohort if they still meet entry criteria.

3.3.2. Blinding and Unblinding

Dosing materials will be prepared by an unblinded study pharmacist, labeled with the subject identifier, and administered by a member of the study team. All dosing materials will have identical appearance and all members of the site study team (apart from the unblinded pharmacist) will be blinded to the treatment assignment, along with the study participants. Apart from the individuals noted above, the Sponsor and CRO personnel will be unblinded, although the blind will be maintained during discussions with the site PI and staff. Subjects and Investigators will remain blinded to the subject's group assignment (PHV01 dose or placebo) until the study database is locked.

Interim Analysis of Safety and of Immunogenicity

One IA will be performed when all 36 subjects have completed the day 29 follow-up. For this IA, the records to be included from each subject will be 'frozen' after being monitored and queries will be resolved without unblinding the site staff. Pre-specified tables, listings, and figures will describe solicited local and systemic AEs, unsolicited AEs, and any MAAEs or SAEs, along with a simple listing of labs by subject without analysis of the latter.

For immunogenicity analyses, tables, listings, and figures will describe the serum IgG ELISA and PsVNA for each Group. In addition, RT-qPCR results from plasma, urine, and saliva samples will be used to assess viremia and shedding. Details regarding the IA for safety, immunogenicity, and sample algorithms will be provided in the Statistical Analysis Plan (SAP).

Individual Subject Unblinding

The group assignment for an individual subject may be unblinded during the course of the study if the PI deems that, for health purposes, the blind must be broken emergently to evaluate an AE;

the other SRC members should be included in the decision if time allows. Only in the case of an emergency, when knowledge of whether the subject has received the IP is essential for the clinical management or welfare of the subject, may the unblinded study pharmacist unblind that subject's treatment assignment. Unblinding at the study site for any other reason other than to confirm rVSV shedding positivity will be considered a protocol violation and reported as a major deviation.

Otherwise, the group assignments will be shared with the site, and subjects will be given the opportunity to request the identity of the IP he or she received, after the conclusion of all study visits (day 1 to 181) and locking of the database.

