3.4. INVESTIGATIONAL PRODUCT

The IP, PHV01, was manufactured under GMP conditions by National Resilience (formerly Ology Bioservices) in Alachua, FL for PHV. Subjects will receive a 1 mL IM injection of PHV01 or placebo, according to the randomization plan. Lactated Ringer's solution USP will be used as the diluent and placebo. Sites will source the Lactated Ringer's solution USP from their pharmacy and will only utilize solution that is approved for parenteral use in humans, noting lot number and certificate of testing. See the Pharmacy Manual for details on the specific lot of IP to be used, the vial label, and methods for preparing dosing materials for administration to study participants.

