5.6.4. Vaccinemia and Shedding

Vaccinemia and shedding will be determined by PHV01 RT-qPCR assay using primer-probe set(s) specific for the vaccine vector VSV.

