7.2. ADMINISTRATIVE INTERIM ANALYSIS

The Sponsor will perform an administrative IA on cleaned and frozen data after all subjects have been vaccinated and observed through the day 29 visit to guide dose selection for a subsequent Phase 2 trial in one or more endemic countries in Africa. The IA will include laboratory measurements through day 29 of seroconversion by ELISA and PsVNA, GMT of the IgG ELISA and PsVNA, and reverse cumulative distribution curves by dose group, with descriptive statistics. Measures of safety through day 29 will include SAEs, MAAEs, AEs, and the frequency and severity of AEs including solicited and unsolicited AEs. Solicited local and

systemic AEs will be collected for days 1-15; solicited AEs for days 16-29 are limited to instances of neurological signs and symptoms, arthritis, and rash. As soon as vaccinemia, shedding, and excretion data are available, they may be added to the IA. Neurologic findings through day 29 will be summarized, including those identified during scheduled neurological examinations at Screening and day 29.

This is a single-blind trial. Summarized results, including treatment assignments of individual subjects, will be provided to the Sponsor and Regulatory Agencies as described in the Unblinding Plan. In addition, selected summarized results by treatment group may be presented at meetings with BARDA, the Phase 2 clinical study sites, and others who are engaged in making strategic decisions on further clinical development of the PHV01 vaccine. The clinical site and subjects will remain blinded until the full data set is cleaned and locked at the end of the trial.

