For hematology and serum chemistry tests, the mean, mean change, median, median change, and range of all values for each test, for each treatment group at baseline and for the final 'on therapy' values, will be printed in a summary table. A second table (a 'shift table') will be made, showing for each laboratory variable the percentage of subjects in each treatment group whose values decreased, stayed the same, or increased between the baseline or pre-treatment period and the end of the study. A third table will be prepared displaying the numbers of subjects in each treatment group who had values below, within, and above the normal range at baseline and at the final visit. Abnormal laboratory measurements that occur following vaccination will be summarized overall and by toxicity grade. A fourth table will be prepared displaying positivity or negativity for rVSV PCR from blood, urine, and saliva; and from other suspect lesions if applicable, on days it is assessed.

These tables will be reviewed by the PI, Medical Monitor, Sponsor, and SRC to evaluate whether any significant trends in laboratory values occurred. The urinalysis data will also be reviewed by inspecting the laboratory data tabulations, but no summary tables of these will be prepared. Vital signs and change from baseline in vital signs will also be summarized at each study visit.

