1.2.3. Stopping Rules and Unblinding

Criteria for Study Pause or Halt

The Safety Review Committee (SRC) will review the Day 8 safety data in each dosing cohort to determine if enrollment may continue. Dosing will be paused if 2 or more subjects experience the same or similar Grade 3 AE considered to be at least possibly related to vaccination. In the event of a study pause, the SRC will meet before resumption of dosing. Dosing will be halted if a serious adverse event (SAE) or an adverse event of special interest (AESI) is considered to be related to PHV01 vaccine. In the event dosing is halted, the SRC and Institutional Review Board (IRB) will review the event and other relevant safety data from the study and the IRB must agree before any continuation of dosing.

Enrollment

If no pause or halting rules are triggered in each dosing cohort, enrollment and dosing may proceed after review of Day 8 safety data by the SRC. In the event dosing is paused or halted, scheduled follow up visits and procedures will continue for subjects already dosed.

Individual Subject Unblinding

The group assignment for an individual subject may be unblinded during the course of the study if the Principal Investigator (PI) deems that, a safety event requires knowledge of that group assignment, the blind must be broken emergently to evaluate an AE; the other SRC members should be included in the decision if time allows. Only in the case of an emergency, when knowledge of whether the subject has received the investigational product (IP) is essential for

the clinical management or welfare of the subject, may the unblinded study pharmacist unblind that subject's treatment assignment. Unblinding at the study site for any other reason will be considered a protocol violation and reported as a major deviation.

Otherwise, the group assignments will be shared with the site, and subjects will be given the opportunity to request the identity of the IP he or she received, after the conclusion of all study visits (Day 1 to 181) and locking of the database.

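### Protocol 3.3.2 permits site unblinding to confirm shedding, SAP 1.2.3 calls the same act a violation, and the route can unblind vaccinees selectively to the staff who judge adverse events

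*Protocol*

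**What the plan says.** Protocol 3.3.2 (Individual Subject Unblinding) gives the ground on which the pharmacist may break a code: "Only in the case of an emergency, when knowledge of whether the subject has received the IP is essential for" the subject's management or welfare. The next sentence adds a second ground: "Unblinding at the study site for any other reason other than to confirm rVSV shedding positivity will be considered a protocol violation". SAP 1.2.3 carries almost the same paragraph, but closes it without the shedding ground: "Unblinding at the study site for any other reason will be considered a protocol violation and reported as a major deviation".

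Two other protocol statements describe a blind with no such opening. Section 3.3.2 also says "Subjects and Investigators will remain blinded to the subject's group assignment (PHV01 dose or placebo) until the study database is locked", and section 7.2 says "The clinical site and subjects will remain blinded until the full data set is cleaned and locked at the end of the trial". The end of 3.3.2 releases assignments to the site only after all visits and lock.

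On the assay and the control, Protocol 5.6.4 states "Vaccinemia and shedding will be determined by PHV01 RT-qPCR assay using primer-probe set(s) specific for the vaccine vector VSV", and Protocol 3.4 states "Lactated Ringer's solution USP will be used as the diluent and placebo".

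**The concern.** A code break meant to confirm shedding is triggered by a positive result, and a positive result is itself tied to treatment arm. The subjects whose codes could be opened this way would be almost entirely vaccinees, and opening the code also reveals the dose. In Cohort 2, for example, Protocol 1.6 doses two PHV01 levels together.

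The people who would learn the assignment are the people whose blinding matters most. Under Protocol 6.4.1 and 6.5 the investigator assigns relatedness and severity to each AE. Relatedness stratifies several primary safety endpoints in Protocol 3.1.1, including serious and medically attended AEs up to day 181. An assessor who knows that a subject received live vaccine may more readily call an event possibly related, and there would be no matching shift in placebo subjects. With only 6 placebo subjects, a few shifted judgements could alter the vaccine-placebo picture.

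The conflict between the documents also leaves it unclear how such a code break should be recorded.

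**Working it through.** The plan gives no figure to reproduce, so the main check is a comparison of texts.

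**1. Permitted grounds for site unblinding.**

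| Source | Emergency | Confirm shedding |
|---|---|---|
| Protocol 3.3.2, pharmacist sentence | yes | no |
| Protocol 3.3.2, following sentence | yes | yes |
| SAP 1.2.3 | yes | no (major deviation) |
| Protocol 3.3.2 and 7.2, blind kept to lock | not addressed | no |

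The SAP revision history lists only changes to the handling of results below the limits of detection and quantitation, so it does not explain the difference. The protocol does not say who may ask for the check, when, what it would confirm, or who would learn the answer.

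**2. Direction.** Placebo is Lactated Ringer's, the assay targets the vector, and exclusion criterion 14 (Protocol 4.5) bars earlier VSV infection and earlier VSV-vectored vaccination. A true positive is therefore expected almost only after PHV01. This is an inference. A false positive, or the contact transmission that Protocol 1.5.9.1 acknowledges as possible, could still make a placebo subject positive.

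**3. Timing.** The exemption has effect only before lock, since assignments are released afterwards anyway. Protocol 5.5.1 has plasma and urine frozen until transfer and saliva frozen pending transport. Protocol 7.2 says shedding data may be added to the day 29 interim analysis once available. Results may therefore arrive after the day 8 reviews and after much of the AE assessment to day 29. Protocol 3.1.3 collects serious, medically attended and special-interest AEs throughout participation, so those assessments can still be open.

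**4. Illustration of how informative a positive is.** The inputs are 30 vaccinees and 6 placebo subjects (Protocol 7.1). The share *s* of vaccinees with a positive and the placebo false-positive rate *f* are assumptions, because the documents give neither.

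- Before any result: P(vaccinee) = 30/36 = 83.3%. In a pioneer set it is 3/4 = 75%, and in a remainder set 7/8 = 87.5%.
- After a positive: P(vaccinee) = 30s / (30s + 6f).
  - f = 0: 100% for any s above 0.
  - s = 0.1, f = 0.05: 3/(3 + 0.3) = 90.9%.
  - s = 0.8, f = 0.01: 24/(24 + 0.06) = 99.8%.
- If every positive subject were unblinded and f = 0, the chance that a subject still blinded is on placebo is 6/(6 + 30(1 − s)). At s = 0.1, 0.2, 0.5 and 0.8 this gives 6/33 = 18.2%, 6/30 = 20.0%, 6/21 = 28.6% and 6/12 = 50.0%, against 6/36 = 16.7% at the start.

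The direction is the same across the range. The size runs from slight to large, depending on a rate that the plan does not supply.

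**5. Need.** Under Protocol 3.3.2, Sponsor and CRO personnel other than the Medical Monitors and the blinded CRA already hold the code. Contact precautions (Protocol 4.4 and 5.3) apply to all subjects whatever their arm. The documents name no step that requires the site to learn the arm of a shedder.

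**The case against.** The strongest reply is that the clause permits unblinding without requiring it, and that nothing shows individual PCR results reaching the site while AEs are being judged. That stands. A reader might infer that the blind is lost during AE assessment. The documents support only that it can be lost, for assessments still open when results come back. The pausing and halting rules in Protocol 3.7.2 govern dosing, so an effect through them would need results before dosing ends, which is not shown.

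It is also fair that the trial is largely descriptive, that the SAP tabulates solicited AEs by term and severity without relatedness, that subjects grade their own symptoms on the Memory Aid, and that a subject is already 83.3% likely to be a vaccinee. These points limit the harm. They do not reach the serious and medically attended AE endpoints, which are stratified by relatedness to day 181.

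SAP 1.2.3 sits in a section that restates the protocol, so it may not be the rule that governs the site. The restatement is then wrong, and the protocol's internal conflict remains.

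Three stronger readings should be set aside:
- Protocol 7.5.1 describes a table of rVSV PCR positivity and adds: "These tables will be reviewed by the PI, Medical Monitor, Sponsor, and SRC to evaluate whether any significant trends in laboratory values occurred". A reader might take this as a second leak to the investigator. The companion tables run to the end of the study and the final visit, so the set reads as end-of-study output.
- A reader might expect unblinded vaccinees to drop out of the per-protocol population. SAP 2.1 excludes only for violations that affect interpretation of immunogenicity, SAP 2.2 leaves the decision to the Sponsor, and Protocol 5.1.5 has titers measured at a laboratory without the code.
- A probability that the Cohort 1 placebo subject is identified by elimination would need a shedding rate, independence between subjects, and a code break for every positive. The documents supply none of these.

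**Conclusion.** The contradiction is certain. Protocol 3.3.2 allows what SAP 1.2.3 classes as a major deviation, and it conflicts with its own emergency-only sentence and with the blinded-to-lock statements in 3.3.2 and 7.2. The one-sided mechanism is well supported: with virus-free placebo and a vector-specific assay, the exemption would open almost only vaccinee codes, false positives and contact transmission aside.

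The consequence is a possibility of selective unblinding of the investigators who judge relatedness and severity, confined to assessments open when results arrive, in particular serious, medically attended and special-interest AEs to day 181. Its size cannot be given, because the plan states neither a shedding rate nor when results return to the site. It is worth correcting because it touches primary safety endpoints and the documents show no need for the exemption.

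**What to change.** Reconcile Protocol 3.3.2, Protocol 7.2 and SAP 1.2.3 so that confirming a shedding result does not unblind site staff who assess AEs. Two forms would do:

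- Remove the shedding exemption from Protocol 3.3.2, and have any code check made by Sponsor or CRO staff who are already unblinded, without passing the assignment to the site.
- Or keep the exemption, state who is unblinded, when and for what purpose, keep AE assessors blind, and carry the same wording into the SAP.

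In either case, state that routine subject-level plasma, urine and saliva RT-qPCR results are not released to AE-assessing site staff before final lock, since a positive result discloses the arm nearly as well as the code does. Leave the existing emergency route and the lesion and joint work-up as the protocol has them. Log every shedding-triggered code break with its date, so that AE relatedness can be reported with and without subjects unblinded before assessment.

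The cost is a deleted or completed clause, a sentence on routing of results, a matching line in the SAP and a log entry if the case arises. The small downside is that the site does not see routine shedding results in real time.
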